Random forest model predicting Pittsburg Sleep Quality Index score change between the final observation and baseline (PSQI\_Delta).

% variation explained: 13.01%

[figure not shown]
- Meaning that ~87% of the variation is unexplained

Here is the plot showing how the model is converging. Better.

Here are the experimental variables that are explaining the most variation or are the most predictive of the PSQI\_Delta score. It is encouraging that MADRA\_Delta score is one of the best predictors of PSQI\_Delta score.

rf

[figure not shown]
Random forest model predicting Length of Stay (LOS).

% variation explained: 18.7%

- Meaning that ~81% of the variation is unexplained

[figure not shown]
Here is the plot showing how the model is converging.

[figure not shown]
Here are the experimental variables that are explaining the most variation or are the most predictive of the LOS.

rf

[figure not shown]

[figure not shown]
[figure not shown]
I made some box plots of the target variables with notches. If the notches are overlapping that means that the difference is not significant.

MADRA\_Delta

HAMAT\_Delta

I also ran some linear models on the target variables to see if there was a significant proportion of the variation explained by the treatment. Here are the various models. A summary of the results is that none of the target variables explained a significant proportion of the variance in the treatment variable. In addition the treatment variable did not explain a significant proportion of the variance in any of the target variables.

Active vs Sham

```
Call:
lm(formula = dat$Active_vs._Sham ~ dat$MADRA_Delta + dat$PSQI_Delta +
    dat$LOS + dat$HAMAT_Delta)

Residuals:
    Min       1Q   Median       3Q      Max
-0.7116 -0.4783  0.1233  0.4296  0.6952

Coefficients:
                Estimate Std. Error t value Pr(>|t|)
(Intercept)    1.680905   0.272114   6.177 1.85e-06 ***
dat$MADRA_Delta -0.008970   0.014086  -0.637   0.530
dat$PSQI_Delta  0.024970   0.021857   1.142   0.264
dat$LOS        -0.014567   0.011225  -1.298   0.206
dat$HAMAT_Delta 0.006887   0.019592   0.352   0.728
---
Signif. codes:  0 '***' 0.001 '**' 0.01 '*' 0.05 '.' 0.1 ' ' 1

Residual standard error: 0.5104 on 25 degrees of freedom
Multiple R-squared:  0.1317,    Adjusted R-squared:  -0.007216
F-statistic: 0.9481 on 4 and 25 DF,  p-value: 0.4529
```

MADRA\_Delta

```

Call:
lm(formula = dat$MADRA_Delta ~ dat$HAMAT_Delta + dat$PSQI_Delta +
    dat$Active_vs._Sham + dat$LOS)

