Residuals:
    Min       1Q   Median       3Q      Max
-19.1440  -4.4362   0.3207   4.8098  13.4379

Coefficients:
                Estimate Std. Error t value Pr(>|t|)
(Intercept)    -4.75714    4.17875  -1.138  0.265741
dat$HAMAT_Delta  0.84571    0.21889   3.864  0.000703 ***
dat$PSQI_Delta  0.65285    0.28752   2.271  0.032044 *
dat$Active_vs._Sham1 -1.77929    2.79430  -0.637  0.530071
dat$LOS         -0.07574    0.16263  -0.466  0.645431
---
Signif. codes:  0 '***' 0.001 '**' 0.01 '*' 0.05 '.' 0.1 ' ' 1

Residual standard error: 7.188 on 25 degrees of freedom
Multiple R-squared:  0.5498,    Adjusted R-squared:  0.4778
F-statistic: 7.633 on 4 and 25 DF,  p-value: 0.0003661

```

HAMAT\_Delta

```

Call:
lm(formula = dat$HAMAT_Delta ~ dat$MADRA_Delta + dat$PSQI_Delta +
    dat$Active_vs._Sham + dat$LOS)

Residuals:
    Min       1Q   Median       3Q      Max
-10.2459  -2.5605   0.1305   1.8374  11.9851

Coefficients:
              Estimate Std. Error t value Pr(>|t|)
(Intercept)   -5.84565    2.86952  -2.037 0.052353 .
dat$MADRA_Delta  0.44207    0.11442   3.864 0.000703 ***
dat$PSQI_Delta  -0.05453    0.22805  -0.239 0.812978
dat$Active_vs._Sham1 0.71411    2.03158   0.352 0.728154
dat$LOS         0.26534    0.10549   2.515 0.018688 *
---
Signif. codes:  0 '***' 0.001 '**' 0.01 '*' 0.05 '.' 0.1 ' ' 1

Residual standard error: 5.197 on 25 degrees of freedom
Multiple R-squared:  0.5646,    Adjusted R-squared:  0.4949
F-statistic: 8.104 on 4 and 25 DF, p-value: 0.000247

```

PSQI\_Delta

```

Call:
lm(formula = dat$PSQI_Delta ~ dat$MADRA_Delta + dat$HAMAT_Delta +
    dat$Active_vs._Sham + dat$LOS)

Residuals:
    Min       1Q   Median       3Q      Max
-11.3494  -2.1282   0.1626   1.9709   9.8305

Coefficients:
              Estimate Std. Error t value Pr(>|t|)
(Intercept)    0.65390    2.71122    0.241  0.811
dat$MADRA_Delta  0.26188    0.11534    2.271  0.032 *
dat$HAMAT_Delta -0.04184    0.17500   -0.239  0.813
dat$Active_vs._Sham1 1.98695    1.73926    1.142  0.264
dat$LOS        -0.04182    0.10311   -0.406  0.688
---
Signif. codes:  0 '***' 0.001 '**' 0.01 '*' 0.05 '.' 0.1 ' ' 1

Residual standard error: 4.553 on 25 degrees of freedom
Multiple R-squared:  0.2684,    Adjusted R-squared:  0.1513
F-statistic: 2.293 on 4 and 25 DF,  p-value: 0.08759

```

LOS

```

Call:
lm(formula = dat$LOS ~ dat$MADRA_Delta + dat$PSQI_Delta + dat$Active_vs._Sham +
    dat$HAMAT_Delta)

Residuals:
    Min       1Q   Median       3Q      Max

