-12.844  -4.353  -2.341   2.845  23.249

Coefficients:
              Estimate Std. Error t value Pr(>|t|)
(Intercept)    20.0404    3.3876   5.916 3.57e-06 ***
dat$MADRA_Delta  -0.1136    0.2438   -0.466  0.6454
dat$PSQI_Delta  -0.1563    0.3854   -0.406  0.6885
dat$Active_vs._Sham1 -4.3329    3.3387   -1.298  0.2062
dat$HAMAT_Delta  0.7611    0.3026    2.515  0.0187 *
---
Signif. codes:  0 '***' 0.001 '**' 0.01 '*' 0.05 '.' 0.1 ' ' 1

Residual standard error: 8.802 on 25 degrees of freedom
Multiple R-squared:  0.3168,    Adjusted R-squared:  0.2075
F-statistic: 2.898 on 4 and 25 DF,  p-value: 0.04239

```

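### The arm-on-outcomes regression repeats the four arm tests of the forward models, and in both directions each arm term is adjusted for other post-randomisation outcomes, so none estimates the randomised effect

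*SAP*

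**What the plan says.** All the text at issue is in the linear-model part of the SAP section headed Random forest results. The stated aim is to see whether treatment explains variation in the target variables.

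Five models follow. The first has arm as the response: "lm(formula = dat$Active_vs._Sham ~ dat$MADRA_Delta + dat$PSQI_Delta", plus length of stay (LOS) and HAMAT change. The other four each take one outcome as the response, with arm and the remaining three outcomes as predictors.

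The results are summarised in two sentences. The first says that "none of the target variables explained a significant proportion of the variance in the treatment variable". The second reads "In addition the treatment variable did not explain a significant proportion of the variance in any of the target variables".

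Every model has 25 residual degrees of freedom. The reversed model prints, for example, "Residual standard error: 0.5104 on 25 degrees of freedom". With five coefficients this means 30 patients in each model.

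**The concern.** There are two faults.

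1. **Duplication.** Arm is fixed by randomisation. A slope of arm on an outcome is not a treatment effect and has no reading in scale points or days. Its t test is also algebraically the same as the test of the arm term in the matching forward model. A reader of the two summary sentences will count two supporting results where there is one set of four tests.

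2. **Conditioning.** This is the more consequential fault, and all five models share it. Each arm term is adjusted for the other three outcomes, all of them measured after randomisation and open to influence by treatment. The arm coefficient then answers a different question: how the arms differ in one outcome among patients alike on the other three. That is not the effect randomisation protects, and its size or sign can differ from the plain arm difference. At stake are the effect estimates a reader would take from this pilot, including LOS, the protocol's secondary outcome.

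**Working it through.** **Inputs.** All are coefficients, standard errors, residual standard errors (RSE) and R-squared values printed in the five SAP models. MADRA is read as MADRS, and HAMAT as the Hamilton Anxiety scale (HAM-A) named in the protocol.

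**Step 1: reproduce the printed tests.** t = b/SE, two-sided on 25 df. For MADRS the reversed model prints "dat$MADRA_Delta -0.008970 0.014086 -0.637 0.530" and the forward model prints "dat$Active_vs._Sham1 -1.77929 2.79430 -0.637 0.530071".

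| Outcome | Reversed b (SE) | Forward arm b (SE) | t, reversed | t, forward | p |
|---|---|---|---|---|---|
| MADRS | -0.008970 (0.014086) | -1.77929 (2.79430) | -0.637 | -0.637 | 0.530 |
| PSQI | 0.024970 (0.021857) | 1.98695 (1.73926) | 1.142 | 1.142 | 0.264 |
| LOS | -0.014567 (0.011225) | -4.3329 (3.3387) | -1.298 | -1.298 | 0.206 |
| HAM-A | 0.006887 (0.019592) | 0.71411 (2.03158) | 0.352 | 0.352 | 0.728 |

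Both directions test one partial correlation, so b(reversed) × b(forward) must equal t²/(t² + 25). The two sides agree: 0.01596 (MADRS), 0.04961 (PSQI), 0.06312 (LOS) and 0.00492 (HAM-A). All four signs agree between directions.

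**Step 2: the joint test.** F = (0.1317/4)/(0.8683/25) = 0.948 on 4 and 25 df, p = 0.453, as printed. No forward model gives this test.

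**Step 3: allocation.** Arm sum of squares = 25 × 0.5104²/(1 - 0.1317) = 7.50. For 30 patients this is n1 × n0/30, and 15 × 15/30 = 7.50; a 14:16 split would give 7.47. So the split is 15:15.

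**Step 4: unadjusted differences.** A least-squares model that contains arm has residuals averaging zero within each arm. The raw arm differences D (level 1 minus level 0) therefore satisfy the forward equations exactly:

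- D(MADRS) = -1.77929 + 0.84571 D(HAM-A) + 0.65285 D(PSQI) - 0.07574 D(LOS)
- D(HAM-A) = 0.71411 + 0.44207 D(MADRS) - 0.05453 D(PSQI) + 0.26534 D(LOS)
- D(PSQI) = 1.98695 + 0.26188 D(MADRS) - 0.04184 D(HAM-A) - 0.04182 D(LOS)
- D(LOS) = -4.3329 - 0.1136 D(MADRS) - 0.1563 D(PSQI) + 0.7611 D(HAM-A)

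The solution is MADRS -1.33, HAM-A -1.47, PSQI +1.93, LOS -5.60. The HAM-A line shows where the sign change arises: 0.714 - 0.589 - 0.105 - 1.486 = -1.47. Most of it comes through LOS.

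**Step 5: intervals.** Total SD = √[25 × RSE²/(1 - R²)/29], which gives 9.95, 7.31, 4.94 and 9.89 for MADRS, HAM-A, PSQI and LOS. Inverting the matrix of printed partial correlations gives marginal correlations with arm of -0.068, -0.102, 0.199 and -0.288, and returns all five printed R-squared values. Then SE = √[SD² × 29 × (1 - r²)/28/7.5], with t(0.975, 28) = 2.048.

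| Outcome | Printed, adjusted for other outcomes | Unadjusted (SE) | 95% CI | p |
|---|---|---|---|---|
| MADRS | -1.78 (p = 0.53) | -1.33 (3.69) | -8.89 to 6.22 | 0.72 |
| HAM-A | +0.71 (p = 0.73) | -1.47 (2.70) | -7.00 to 4.07 | 0.59 |
| PSQI | +1.99 (p = 0.26) | +1.93 (1.80) | -1.75 to 5.62 | 0.29 |
| LOS, days | -4.33 (p = 0.21) | -5.60 (3.52) | -12.81 to 1.61 | 0.12 |

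For LOS the printed figure is (5.60 - 4.33)/5.60 = 23% smaller than the plain difference.

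**The case against.** The strongest reply is that nothing of consequence changes. The forward models already give the four tests in points and days, dropping the reversed model alters no estimate or p value, and the unadjusted contrasts run from p = 0.12 to 0.72. This stands as far as it goes: deleting the reversed model alone is tidying. What changes the reported effects is taking the other outcomes out of the forward models.

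It is also fair to say that the reversed model is not wholly redundant. Its overall F is a valid joint comparison of the two arms. But the summary sentence speaks of the separate target variables, which are the duplicated tests.

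Several stronger readings are tempting and are not supported:

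- **That the reversed model contradicts the forward model on anxiety.** Both coefficients are positive (+0.0069 and +0.71), as they must be. The change of sign is against the unadjusted difference and comes from the outcome covariates, which the forward model has too.
- **That the SAP misstates the direction of an effect.** It claims no direction for any outcome, both anxiety estimates are far from significant, and the visible text does not say which arm is level 1.
- **That the SAP claims two independent lines of evidence.** It does not use that word; the impression comes from presenting the second sentence as an addition to the first.
- **That these two sentences are its only efficacy conclusion.** It also offers notched box plots and a forest predicting arm, and part of the SAP was not available for this review.

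**Conclusion.** The point holds in two parts. The four coefficient tests in the reversed model are the four arm tests of the forward models, so the two summary sentences report one set of tests twice; only the global F (p = 0.45) is additional. And no printed arm term estimates the randomised difference, because each is conditional on the other outcomes. Removing that conditioning moves HAM-A from +0.71 to -1.47 points and LOS from -4.33 to -5.60 days. MADRS moves from -1.78 to -1.33, and PSQI hardly changes (+1.99 to +1.93).

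The finding of no significant difference is unaffected, and all four intervals are wide and include zero.

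The rebuilt figures assume that the five models use the same 30 patients, which the common 25 residual df and the agreement of all printed R-squared values support. They are unadjusted for baseline. A baseline-adjusted effect cannot be recovered from the printed output.

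**What to change.** 1. Remove the other outcomes from every model meant to estimate an arm effect. Fit MADRS, HAM-A and PSQI each on arm with that scale's own baseline score as covariate, and LOS on arm alone.
2. Report each arm effect with its 95% CI in points or days, and state which arm is the reference level.
3. Delete the sentence saying that the outcomes do not explain variance in treatment, and drop the coefficient table of the reversed model.
4. If a joint test is wanted, keep only the overall F (0.948 on 4 and 25 df, p = 0.45), labelled as a single global test of the four outcomes.

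The cost is a few lines of R, a short text edit and changed reported figures. The protocol already schedules the rating scales at baseline, so no new data collection should be needed for these four models.

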Study Protocol

Protocol Title: Cranial electric stimulation (CES) to modify suicide risk factors in psychiatric inpatients

Study No.: HP-00065640, Date 6th February 2016

Principal Investigator: [name] MD, [contact], [contact] (24 hour access)

Brief Summary

This pilot study aims to investigate whether a treatment called cranial electric stimulation or CES can decrease risk factors for suicide. The specific CES device we will use is called Alpha-Stim®. CES will be used in addition to usual treatment (medication and group therapy).

Detailed Description

Suicide is still a major issue in the United States and all around the world. There are many reasons for people attempting suicide and the major modifiable risk factors are depression, anxiety, insomnia, and agitation. The standard treatment for all suicidal patients includes medication, admission to a hospital and reducing the risk factors. Medications have potential side effects and concerns about the drug interactions. One of the biological treatment alternatives to medication is cranial electric stimulation. This technique uses a device to stimulate the brain through electrical current. Using an Alpha-Stim® device, current is applied to the brain using skin electrodes which can be easily clipped on to the earlobe. The amount of current used is very low and is 1/1000th of the current used for electroconvulsive therapy (ECT) and 1/10th to 1/20th of the 1-2 milli amperes used with transcranial direct current stimulation (tDCS). Our goal is to examine the safety and efficacy of this device when used as an add-on or adjunctive treatment to the usual treatments during the inpatient stay.

Study Type: Interventional

Study Phase: 4

Study Design

Allocation: Randomized Intervention Model: Parallel Assignment

Masking: Double Blind (Participant, Care Provider, Investigator, Outcomes Assessor)

Primary Purpose: Treatment

Conditions:

- Suicide
- Depression

- Anxiety
- Insomnia
- Agitation

Intervention Device: Alpha-Stim®. Study Arms • Experimental: Adjunctive CES

CES 100µA for one hour daily, five to seven days per week. Rating scales will be administered at baseline (i.e., pre-treatment), twice a week and at the end of the study.

Intervention: Device: Alpha-Stim®.

Sham Comparator: Sham control CES

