For the sham group the Alpha-Stim® will not emit electricity. All other procedures will be the same for both the sham group and the active CES group. The current intensity will be preset and locked by the manufacturer. The sham devices will appear identical to the active device.

Intervention: Device: Alpha-Stim

Primary Outcome Measures:

Change in the modifiable suicide risk factors (MSRF's)

To assess the efficacy of adjunctive cranial electric stimulation (CES), specifically Alpha-Stim®, to reduce suicide risk in psychiatric inpatients through a randomized, double-blind, sham-controlled, clinical trial. The primary efficacy outcome measure will be change in the modifiable suicide risk factors (MSRF's) as indicated by a summed global score from rating scales measuring the MSRFs that include depression (Montgomery-Åsberg Depression Rating Scale), anxiety (Hamilton Anxiety Rating Scale), insomnia (The Pittsburgh Sleep Quality Index) and agitation (Agitated Behavior Scale).

Assess adverse effects and safety

To assess safety of adjunctive cranial electric stimulation (CES), specifically Alpha-Stim®, to reduce suicide risk in psychiatric inpatients through a randomized, double-blind, sham-controlled, clinical trial. The primary safety outcome measure will be responses to an adverse effect assessment questionnaire (GASE questionnaire).

Secondary Outcome Measures:

Assess length of stay

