### **Random forest results:**

[figure not shown]
All random forest models were run to create 2001 trees.

*Random forest model predicting treatment group (Active vs Sham)*

[figure not shown]
OOB (out-of-bag) error rate: 60%

- This means that the model was wrong 60% of the time and correct 40% of the time.

Here is a plot showing how the model is converging as the number of trees increases. Overall this is the inverse of what you would want to see. Optimally you want the error to start high and decrease to a convergence or a plateau as the number of trees increases. The convergence is settling at an error of  $\sim 0.6$ , which is your OOB error rate.

[figure not shown]

For reference this is what a more favorable plot looks like. This plot has an OOB error rate of 5.73%.

Back to your data, here are the experimental variables that are most predictive of treatment group. There are 2 accuracy metrics here that are used interchangeably based on the preference of the investigator. The accuracy numbers are a bit arbitrary and there is no threshold of significance per se. These are simply the most predictive variables of the target experimental variable.

rf

[figure not shown]
*Random forest model predicting Montgomery-Asberg Depression Scale change between the final observation and baseline (MADRA\_Delta)*

The MADRA\_Delta score is continuous; therefore, the model produces a % variation explained rather than an OOB error rate.

[figure not shown]
% variation explained: 14.14%

- Meaning that ~85% of the variation is unexplained

Here is the plot showing how the model is converging. Again the model is not converging very well.

Here are the experimental variables that are explaining the most variation or are the most predictive of the MADRA\_Delta score. It is encouraging that HAMAT\_Delta score and PSQI-Delta score are two of the best predictors of MADRA\_Delta score.

[figure not shown]

*Random forest model predicting Hamilton Depression Score change between the final observation and baseline (HAMAT\_Delta)*

% variation explained: 0.83%

[figure not shown]
- Meaning that ~99% of the variation is unexplained

Here is the plot showing how the model is converging. Again the model is not converging very well.

Here are the experimental variables that are explaining the most variation or are the most predictive of the HAMAT\_Delta score. It is encouraging that MADRA\_Delta score is one of the best predictors of HAMAT\_Delta score.

rf

[figure not shown]

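### The linear models for MADRS, HAM-A and PSQI change adjust for other post-randomisation outcomes and leave out the scale's own baseline, so their arm coefficients are not treatment effects.

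*SAP*

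**What the plan says.** The SAP's linear models follow the random forests under the heading Random forest results. Their stated purpose is to see whether treatment explains variation in the targets, and the SAP concludes that it does so significantly for none of them. The outcomes are change scores, for example "Montgomery-Asberg Depression Scale change between the final observation and baseline". The three formulas begin:

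- MADRS: "lm(formula = dat$MADRA_Delta ~ dat$HAMAT_Delta + dat$PSQI_Delta"
- HAM-A: "lm(formula = dat$HAMAT_Delta ~ dat$MADRA_Delta + dat$PSQI_Delta"
- PSQI: "lm(formula = dat$PSQI_Delta ~ dat$MADRA_Delta + dat$HAMAT_Delta"

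Each then adds arm and length of stay (LOS). The MADRS arm row reads "dat$Active_vs._Sham1 -1.77929 2.79430 -0.637 0.530071" and the HAM-A row "dat$Active_vs._Sham1 0.71411 2.03158 0.352 0.728154".

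The Protocol's Study Arms entry states "Rating scales will be administered at baseline (i.e., pre-treatment), twice a week and at the end of the study", so baseline scores exist. Its Primary Outcome Measures define efficacy "as indicated by a summed global score from rating scales measuring the MSRFs", which makes MADRS, HAM-A and PSQI components of the primary outcome. LOS is the secondary outcome.

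**The concern.** A covariate in a treatment comparison should be fixed before randomisation. Here each scale is adjusted for change in the other two and for LOS, all of which treatment could affect. If stimulation lowered depression and anxiety together, holding anxiety change constant would remove part of its effect on depression. The coefficient then answers a different question, and its SE belongs to that question too.

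The own-baseline score, which would be a legitimate and usually useful covariate, is absent. A change score uses baseline by subtraction with a fixed slope of one. That does not adjust for starting level as a covariate would.

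This is a pilot, so its estimates and SEs may be carried into later planning. A reader who takes the printed figures as treatment effects would carry forward too small an SE for MADRS and HAM-A and, for HAM-A, the opposite sign.

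**Working it through.** **Inputs.** All come from the SAP's printed regressions: coefficients, SEs, R-squared values, residual standard errors (RSE) and 25 residual df. Five coefficients plus 25 df give n = 30. `HAMAT_Delta` is taken as the Protocol's Hamilton Anxiety scale, although the SAP caption calls it a depression score. The visible text does not say which arm is coded 1, so signs are arm coded 1 minus the other arm and no direction of benefit is inferred.

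**1. Reproduce the printed arm tests** (t = estimate/SE, 25 df).

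- MADRS: -1.77929/2.79430 = -0.637, p = 0.530
- HAM-A: 0.71411/2.03158 = 0.352, p = 0.728
- PSQI: 1.98695/1.73926 = 1.142, p = 0.264

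All agree with the SAP.

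**2. Recover the cross-products.** The five models regress each of arm (A), MADRS (M), HAM-A (H), PSQI (P) and LOS (L) on the other four. They therefore determine the inverse cross-product matrix K:

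K_ii = 1/(25 × RSE_i²), K_ij = -b_ij × K_ii, S = K⁻¹.

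For example, K_AA = 1/(25 × 0.5104²) = 0.15355. K_AM from the arm model is 0.008970 × 0.15355 = 0.001377. From the MADRS model it is 1.77929/(25 × 7.188²) = 0.001377.

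Checks:

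- The two halves of K agree to a relative 0.0003.
- 1 - 1/(S_ii K_ii) returns the printed R-squared values: 0.1317, 0.5498, 0.5646, 0.2684 and 0.3168.
- S_AA = 7.50 = 15 × 15/30, so there are 15 patients per arm.

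**3. Arm comparison of change without the other outcomes.** Difference = S_iA/S_AA; SE = √{[(S_ii - S_iA²/S_AA)/28]/S_AA}; 28 df.

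| Scale | S_iA | S_ii | Difference | SE | 95% CI | p | Printed (SE) |
|---|---|---|---|---|---|---|---|
| MADRS | -10.00 | 2869.1 | -1.33 | 3.69 | -8.89 to 6.22 | 0.72 | -1.78 (2.79) |
| HAM-A | -11.00 | 1550.6 | -1.47 | 2.70 | -7.00 to 4.07 | 0.59 | +0.71 (2.03) |
| PSQI | 14.50 | 708.4 | +1.93 | 1.80 | -1.75 to 5.62 | 0.29 | +1.99 (1.74) |

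MADRS in full: -10.00/7.50 = -1.33, and √{[(2869.1 - 13.3)/28]/7.50} = 3.69. Rounding in the printed output moves the differences by less than 0.002.

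**4. Why the HAM-A sign changes.** The same matrix gives a LOS difference of -5.60. The simple HAM-A difference equals the printed coefficient plus each covariate's slope times its own arm difference:

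0.714 + 0.44207 × (-1.333) - 0.05453 × 1.933 + 0.26534 × (-5.599) = 0.714 - 0.589 - 0.105 - 1.486 = -1.47.

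Conditioning on MADRS change and LOS takes out most of what separates the two figures.

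**5. Expected effect of adding own baseline.** The baseline-final correlation r is not in the documents, so a range is assumed. With equal baseline and final variances, variance relative to simple change is (1 + r)/2 × 27/26. The last factor is the small-sample cost of one covariate.

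| r | Variance ratio | SE reduction | MADRS SE | HAM-A SE | PSQI SE | Equivalent n per arm (15/ratio) |
|---|---|---|---|---|---|---|
| 0.3 | 0.675 | 18% | 3.03 | 2.22 | 1.48 | 22 |
| 0.5 | 0.779 | 12% | 3.25 | 2.39 | 1.59 | 19 |
| 0.7 | 0.883 | 6% | 3.46 | 2.54 | 1.69 | 17 |
| 0.9 | 0.987 | 1% | 3.66 | 2.68 | 1.79 | 15 |

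Break-even is r = 2 × 26/27 - 1 = 0.93.

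With k = final SD/baseline SD, the ratio is k²(1 - r²)/(1 + k² - 2rk) × 27/26. For MADRS at r = 0.3, 0.5 and 0.7:

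- k = 0.8: SE 2.66, 2.84 and 2.98.
- k = 1.25: SE 3.33, 3.55 and 3.72, so no gain at r = 0.7.
- k = 1.5: ratio 1.001 at r = 0.5, so no gain there.

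**The case against.** The strongest reply is that nothing of consequence changes. All three comparisons are non-significant with or without the extra covariates. The two HAM-A figures have t = 0.35 and t = -0.54, so the sign change lies within noise. The SAP also prints the regression of arm on all four outcomes (F = 0.9481 on 4 and 25 df, p = 0.4529). With two arms this is a joint test of any difference, free of the conditioning problem. All of this is correct. But a joint test gives no effect or interval for any one scale, and the per-scale coefficients remain estimates of the wrong quantity.

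A second reply is that unadjusted change is already unbiased under randomisation, so baseline adjustment is only a matter of efficiency, and the size of the gain cannot be known here. That is right. Chance imbalance is a conditional error in this one trial, not a bias over repeated randomisations, and the actual imbalance is not visible. The baseline part of the point is an improvement in precision; the post-randomisation covariates are the error, and that does not depend on r.

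Third, part of the SAP before its Method section was not available, the figures are missing and the random forest predictors are not shown. A baseline-adjusted analysis elsewhere cannot be excluded. The point is therefore limited to the printed linear models.

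**Conclusion.** The concern holds for the three printed models. Their arm coefficients are not treatment effects on the scales, and the SAP's per-scale statement about treatment should not rest on them. The printed SEs are about 24% (MADRS), 25% (HAM-A) and 3% (PSQI) below those of the simple comparison, because they belong to a different quantity. The simple comparison needs no assumption beyond the printed output.

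The further gain from own baseline rests on the assumed r and variance ratio; it is probably modest and could be nil. The null conclusion may well survive. If the point estimates stayed where they are, p on 27 df would be about 0.66, 0.51 and 0.20 (MADRS, HAM-A, PSQI) at r = 0.3, and 0.70, 0.57 and 0.26 at r = 0.7. These are illustrations, not forecasts, because adjustment also moves the estimates.

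**What to change.** Replace each formula with final score (or change) on arm plus the baseline of the same scale, and drop the other change scores and LOS as covariates. Report the adjusted arm difference with its 95% CI and state which arm is coded 1. Because results are already known, label these as corrected or sensitivity analyses.

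The cost is three short refits. The baseline scores must already be held, since the changes are computed from them. Each model has two predictors instead of four, so residual df rise from 25 to 27.

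As a secondary addition, fit the same model to the Protocol's summed risk-factor score with its own baseline sum. That also needs the Agitated Behavior Scale, which the Protocol lists but no printed linear model uses.

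### Each visible SAP outcome model adjusts for the other three post-randomisation outcomes, so its treatment coefficient is not the randomised active-versus-sham difference

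*SAP*

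**What the plan says.** In the SAP section *Random forest results*, after the box plots, the author introduces linear models of the target variables. Their purpose is "to see if there was a significant proportion of the variation explained by the treatment", and the summary is that treatment explains no significant share of the variance in any target.

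The printed calls are:
- MADRS change: "lm(formula = dat$MADRA_Delta ~ dat$HAMAT_Delta + dat$PSQI_Delta", plus arm and LOS.
- Hamilton change: "lm(formula = dat$HAMAT_Delta ~ dat$MADRA_Delta + dat$PSQI_Delta", plus arm and LOS.
- PSQI change: "lm(formula = dat$PSQI_Delta ~ dat$MADRA_Delta + dat$HAMAT_Delta", plus arm and LOS.
- Length of stay: "lm(formula = dat$LOS ~ dat$MADRA_Delta + dat$PSQI_Delta + dat$Active_vs._Sham", plus the Hamilton change.

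A fifth model reverses the roles and regresses arm on all four targets ("F-statistic: 0.9481 on 4 and 25 DF", p = 0.4529).

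The SAP defines each Delta as the change between the final observation and baseline. The protocol describes a randomised, sham-controlled trial. It lists the rating scales under *Primary Outcome Measures* and length of stay under *Secondary Outcome Measures*.

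The SAP describes `HAMAT_Delta` as "predicting Hamilton Depression Score change between the final observation and baseline", whereas the protocol names the Hamilton Anxiety scale. I take the variable to be the anxiety scale.

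**The concern.** Randomisation protects the comparison of arms as a whole, or within levels of variables fixed before allocation. It does not protect a comparison among patients matched on what happened afterwards. All four targets are post-randomisation outcomes. The arm coefficient in each model is therefore the difference that remains once the other outcomes are held equal, not the total effect of CES. If CES moves the other outcomes, the coefficient is biased for that total effect; the data do not show whether it does.

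Two consequences follow. The share of variation explained by treatment, which is what the SAP says it examined, is not what the models measure. And in a 30-patient pilot, the estimates and standard errors that a reader would carry into planning a later trial belong to a different quantity.

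If LOS was included to allow for final ratings taken at different times, that does not help, because LOS is itself an outcome. The overall F-tests of the outcome models (p = 0.0003661, 0.000247, 0.08759 and 0.04239 for MADRS, Hamilton, PSQI and LOS) do not give the treatment share either, because they test all four regressors together.

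**Working it through.** **Inputs.** Coefficients, standard errors, residual standard errors (25 df) and R-squared from the five printed models. With five parameters each, n = 30.

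**1. Reproduce the printed tests.** For the Hamilton model, t = 0.71411/2.03158 = 0.352, p = 0.728 on 25 df, as printed. The MADRS, PSQI and LOS arm terms also reproduce (p = 0.530, 0.264, 0.206).

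**2. Recover the unadjusted quantities.** Let S be the matrix of centred sums of squares and products for arm (T) and the four outcomes. Regressing variable i on the other four gives row i of the inverse of S: diagonal 1/RSS_i and off-diagonal -b_ij/RSS_i, with RSS_i = 25 x s_i^2. The RSS values are:
- arm: 25 x 0.5104^2 = 6.513
- MADRS: 25 x 7.188^2 = 1291.68
- Hamilton: 25 x 5.197^2 = 675.22
- PSQI: 25 x 4.553^2 = 518.25
- LOS: 25 x 8.802^2 = 1936.88

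Each off-diagonal is available twice. For arm and Hamilton, -0.71411/675.22 = -0.0010576 and -0.006887/6.513 = -0.0010575. Over all pairs the two versions agree within 0.031%.

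**3. Check the inversion.** The treatment sum of squares comes out at 7.50 = 15 x 15/30, so 15 per arm. Total sums of squares match RSS/(1 - R2) within 0.02% (MADRS 2869.10 against 2869.13). The recovered differences times 15 are -20, -22, 29 and -84 to rounding, as expected for whole-number scores with 15 per arm.

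**4. Unadjusted contrasts.** Difference = S_TY/S_TT; residual SS = S_YY - S_TY^2/S_TT on 28 df; SE = residual SD/sqrt(7.50). For Hamilton, S_TY = -1.466 x 7.50 = -11.0. The residual SS is 1550.6 - 11.0^2/7.50 = 1534.5, the SD is sqrt(1534.5/28) = 7.40, and the SE is 7.40/2.739 = 2.70.

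The share for treatment alone is S_TY^2/(S_TT x S_YY). The treatment increment in the printed model is t^2 x (1 - R2)/25. For LOS the increment is 1.298^2 x 0.6832/25 = 4.6%.

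Signs are level 1 minus reference; the output does not show which arm is level 1.

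| Outcome | Unadjusted (SE; 95% CI; p) | Printed (SE; 95% CI; p) | Share alone vs increment |
|---|---|---|---|
| Hamilton | -1.47 (2.70; -7.00 to 4.07; 0.59) | +0.71 (2.03; -3.47 to 4.90; 0.73) | 1.0% vs 0.2% |
| MADRS | -1.33 (3.69; -8.89 to 6.22; 0.72) | -1.78 (2.79; -7.53 to 3.98; 0.53) | 0.5% vs 0.7% |
| PSQI | +1.93 (1.80; -1.75 to 5.62; 0.29) | +1.99 (1.74; -1.60 to 5.57; 0.26) | 4.0% vs 3.8% |
| LOS | -5.60 (3.52; -12.81 to 1.61; 0.12) | -4.33 (3.34; -11.21 to 2.54; 0.21) | 8.3% vs 4.6% |

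**5. Why the Hamilton estimate moves.** -1.466 - (0.4421 x -1.333) - (-0.0545 x 1.933) - (0.2653 x -5.599) = +0.714. Of the shift of 2.18, LOS contributes 1.49, MADRS 0.59 and PSQI 0.10. In 20,000 simulated trials with no effect and the recovered within-arm covariance, 28% gave opposite signs, so the sign change itself is within noise.

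**6. What the models could hide (assumption, not shown by the data).** Suppose CES shifted all three scales by one within-arm SD (MADRS 10.10, Hamilton 7.40, PSQI 4.93) and left LOS alone. The fractions retained would be:
- MADRS: 1 - (0.84571 x 7.40 + 0.65285 x 4.93)/10.10 = 6%
- Hamilton: 1 - (0.44207 x 10.10 - 0.05453 x 4.93)/7.40 = 43%
- PSQI: 1 - (0.26188 x 10.10 - 0.04184 x 7.40)/4.93 = 53%

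The 95% sampling ranges are wide: about -18 to 35%, 19 to 74% and 19 to 96%. If CES moved only MADRS, the MADRS model would retain 100%.

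**The case against.** The strongest reply is that no conclusion changes. The SAP claims only non-significance, and the unadjusted p-values (0.12 to 0.72) agree. The reverse model's overall F is also a legitimate joint test of arm across the four outcomes: the equivalent Hotelling T2 is 4.247, and 4.247 x 25/(28 x 4) = 0.948. Both statements are correct. But the joint test gives no effect for any single outcome, and the reverse model's four t values repeat the outcome models' treatment tests.

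It can also be said that a coefficient t-test validly tests incremental variation, and that the SAP never promises an unconditional share. Even so, the text names variation explained by treatment and does not say that it is conditional on other outcomes.

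The notched box plots appear, from context, to compare the arms without adjustment. They belong in any account of what was done, but the notch rule supplies no estimate, standard error or p-value.

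Three limits stand. The changes do not all go one way: the treatment share falls for Hamilton and LOS, rises slightly for MADRS and barely moves for PSQI. The retained fractions are hypothetical. And these models do not analyse the protocol's summed-score primary outcome, so their weight within the full plan is uncertain.

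**Conclusion.** The concern holds and should be fixed. As written, none of the four outcome models estimates the randomised comparison. The unadjusted SE is 32% larger than printed for MADRS (3.69 against 2.79) and 33% larger for Hamilton (2.70 against 2.03). The LOS difference is 1.27 larger in size than printed (5.60 against 4.33), and PSQI is nearly unaffected. The finding of non-significance survives for every outcome; the point estimates, intervals and explained shares do not.

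This rests on the same 30 patients entering all five models, which the matching degrees of freedom and the near-exact symmetry of the reconstruction support. It also assumes that `HAMAT_Delta` is the anxiety scale. An earlier part of the SAP and all figures were unavailable, so simple arm comparisons may exist elsewhere; the verdict covers the visible linear models only.

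**What to change.** Remove the other Delta variables and LOS from the right-hand side of each outcome model.

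- **Symptom scales:** regress each change on randomised arm plus that scale's own baseline. Arm alone already removes the defect; baseline is added for precision.
- **LOS:** regress on arm with pre-randomisation covariates only. The printed residuals run from -12.8 to 23.2 with median -2.3, which suggests skew, so give a permutation p-value beside the mean difference. This is a precaution: in simulations with skewed LOS the t-test error rate was 4.1 to 4.6%.
- **Reporting:** give each arm difference with a 95% CI, state which level is active, and say that final observations may fall at different times for different patients.
- **Reverse model:** keep it only for its overall F, as one approximate global test, and say that its four t values add nothing to the outcome models.

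The cost is four short reruns and a text edit. Baseline scores are already held, since every Delta was computed from them.

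The likely downside is precision. The baseline-adjusted SE cannot be computed from the documents. Taking it as unadjusted SE x sqrt((1 - r^2) x 28/27), and assuming a within-arm baseline-change correlation r of 0.3, 0.5 or 0.7 in size, it would be 3.58, 3.25 or 2.68 for MADRS; 2.63, 2.38 or 1.97 for Hamilton; and 1.75, 1.59 or 1.31 for PSQI. It equals the printed SE at r of about 0.67 for MADRS and Hamilton and 0.32 for PSQI, so the corrected analysis could be less or more precise than the printed one.

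These changes do not supply the summed-score primary analysis named in the protocol.
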